**2.3.** A simple novel approach noted improvement of BMV in the bearded patient  by placing a large (6 x 8 inch) Tegaderm™ across the lower face to improve face-to-mask seal, after first cutting a hole in the device to permit passage of air and instruments. To date, evidence for improved facemask seal in the bearded patient has only been anecdotal. We plan on studying a heretofore non-studied technique involving application of a large Tegaderm™ across the lower face of the bearded patient to quantify its effectiveness at improving mask ventilation in this anesthetized population. This technique can be applied rapidly, without dramatic head manipulation, preserving effective grip, and can be adopted across multiple healthcare modalities, making it a worthy intervention to explore in detail. By quantifying the effectiveness of this intervention, we hope this study can be used to inform guidelines for the management of difficult BMV in the bearded patient.

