## 7. Study Endpoints

7.1. *Describe the primary and secondary study endpoints.*

Primary outcome: Mask leakage, defined as the difference between average inspired and expired tidal volumes, as a percentage of inspired volume. Patients will serve as their own controls; the comparison is of the difference in leakage in the Tegaderm™ versus baseline conditions.

Secondary outcomes: 1. Difference in airway resistance between Tegaderm™ and baseline conditions, 2. Difference in peak inspiratory pressure between Tegaderm™ and baseline conditions, 3. Extent to which mask leakage change with Tegaderm™ depends on beard length.

7.2. *Describe any primary or secondary safety endpoints.*

If bag/mask ventilation is difficult and a Tegaderm™ not already in place, one will be placed in an effort to provide a better seal for the mask. If ventilation continues to be difficult, an Attending Anesthesiologist would attempt bag mask ventilation, consider placing an oral airway, and follow the difficult airway algorithm (6) by using supraglottic airway as a rescue device if deemed necessary. This event will be considered data and included in analyses.

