## 13. Data Analysis

13.1. *Describe the data analysis plan, including any statistical procedures.*

Paired data (within patient differences in leakage,  $PP_{ins}$ , and airway resistance) will be assessed with paired t-test or Wilcoxon rank-sum test, depending on distribution normality. Beard condition groups will be compared on the primary outcome (leakage difference  $> 15\%$  significant) with ANOVA or Kruskal-Wallis test, also depending on distribution normality. Sensitivity analysis will provide percentage of observed standard deviation for detection of leakage difference and a traditional power analysis to provide the sample size required to detect significant outcome with our intervention.

13.2. *Provide a power analysis, if applicable*

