## Tegaderm™ Placement for Bag Mask Ventilation in the Bearded Patient

The data and statistics that would be required for a formal sample-size calculation with a reliable power estimate are not available. For that reason, the investigators plan a 2-phase process. In the first (external pilot) phase, the investigators plan to enroll 25 participants following a published guideline (Whitehead AL, et al. *Statistical Methods in Medical Research* 2016; 25:1057-73) and use the generated data to obtain effect-size and standard deviation information. Those statistics will permit a valid sample size calculation for the second phase, i.e. the main trial. The investigators will submit a modification to HRRC with sample size justification for the main trial prior to enrolling any patients for it.

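### A normality check picks the primary test and no estimate or interval is planned, so the reported quantity can change after the data are seen and may not match a mean-based sample size

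*Combined protocol and SAP*

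**What the plan says.** Section 7.1 defines the primary outcome as "Mask leakage, defined as the difference between average inspired and expired tidal volumes, as a percentage of inspired volume" and adds that "the comparison is of the difference in leakage in the Tegaderm™ versus baseline conditions". It names no population summary such as a mean, median or pseudo-median.

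Section 13.1 covers the primary outcome and two secondary outcomes (peak inspiratory pressure and airway resistance) in one sentence. It opens "Paired data (within patient differences in leakage" and says these "will be assessed with paired t-test or Wilcoxon rank-sum test, depending on distribution normality". The beard-group comparison has the same structure, with ANOVA or Kruskal-Wallis chosen by normality. The plan does not say how normality is judged, or whether pilot or main-phase data decide.

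Apart from tests, 13.1 offers a sensitivity analysis expressed in terms of the standard deviation and "a traditional power analysis to provide the sample size required to detect significant outcome with our intervention". Section 13.2 explains that "The data and statistics that would be required for a formal sample-size calculation with a reliable power estimate are not available", and that the 25-patient pilot will fill the gap: the investigators will "use the generated data to obtain effect-size and standard deviation information". Section 2.3 states the purpose of the study as "to quantify its effectiveness at improving mask ventilation in this anesthetized population". No confidence interval is mentioned anywhere.

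**The concern.** A paired t-test addresses the mean change in leakage. A paired rank test addresses the pseudo-median, that is, the median of all pairwise averages of the differences. The two agree for symmetric differences and separate when a minority of patients gain a lot and most change little. That pattern is plausible here. Leakage is a bounded percentage, operators use a two-handed grip, so many patients may have little leak to remove, and section 12.1 also provides for patients in whom no seal is obtained.

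Three things are at stake. The target of the primary analysis is settled only after the data are seen. The pilot and the main phase could report different quantities. And power computed from a mean and standard deviation belongs to the t-test, whichever test is then run. The test named as the alternative adds a further difficulty, because the rank-sum test is for independent samples and discards the pairing.

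**Working it through.** The plan has no powered figure to reproduce. The 25 is a pilot size, the 50 in section 5.3 is an enrolment ceiling, and no alpha, power, effect or standard deviation is given. Every input below is therefore an assumption: two-sided 5% tests, a Shapiro-Wilk check at 5%, and n=25 and n=50 as illustrative analysis sizes. Simulations used up to 4,000 trials per cell, and ranges show repeat runs.

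**1. A skewed example.** Let the gain (reduction in percent leakage) be N(20, SD 10) in 20% of patients and N(1, SD 6) in 80%.

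- Mean: 0.2×20 + 0.8×1 = 4.8 points.
- Variance: 0.2×(100+400) + 0.8×(36+1) − 4.8² = 100 + 29.6 − 23.04 = 106.56, so SD = 10.3 and the standardized effect is 4.8/10.3 = 0.47.
- Pseudo-median about 3.5 points and median about 2.7 points, both by simulation.

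The same trial would thus centre on 4.8 or about 3.5 points, depending on the check.

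**2. The rule with a signed-rank alternative.**

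| n | Test switches | Power, rule | Power, fixed t-test |
|---|---|---|---|
| 25 | about 58% | 52–55% | 61–64% |
| 50 | about 88% | 83–84% | 94% |

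The switch rate rises with n for the same distribution. For an independent pilot of 25 and a phase of 50, the chance that the two use different tests is 0.58×0.12 + 0.42×0.88 = 0.07 + 0.37 = 0.44.

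**3. The rule with the rank-sum test as named.** The two conditions are compared as if they were independent samples, with baseline leak drawn as N(25, SD s) independently of the gain. With s=12, power under the rule is about 28% at both sizes. It depends on s:

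| s | n=25 | n=50 |
|---|---|---|
| 5 | 39% | 62% |
| 10 | 31% | 37% |
| 15 | 28% | 17% |

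**4. Other skewed shapes, n=34, true mean 0.5 SD, signed-rank alternative.**

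| Shape | Pseudo-median | Switches | Power, rule | Power, t-test |
|---|---|---|---|---|
| Gamma (shape 2) | 0.38 SD | 81% | 71% | 87% |
| Lognormal | 0.32 SD | 98% | 86% | 95% |
| 30% large responders | 0.29 SD | 100% | 41% | 88% |

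**5. Where the rule does little or helps (signed-rank alternative).**

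- Normal differences, n=34, effect 0.5 SD: 80.9% for both. For 80% power at that effect, N is 34 for the t-test and 34/0.955, so 36, for the signed-rank test.
- Mild mixtures (most gain 3 points, SD 6; 20–40% gain 10–15 points, SD 8): under 1 percentage point lost, for example 85.5% against 86.1% at n=25.
- Symmetric heavy tails (t with 3 df), n=25: 80.0% under the rule against 69.6% for the t-test.

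**The case against.** The best case for the plan is that the harm is conditional. The documents give no leakage distribution, and the large losses need strong skew. Under normality or mild skew the rule costs almost nothing, and under symmetric heavy tails it gains power. All of that stands and limits the weight of the power figures. It does not supply a named summary measure or say who judges normality, when, and on which data.

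Two further objections concern scope. Section 7.1 does define a within-patient difference, and 13.2 does plan an effect size and standard deviation from the pilot, so a reader might infer too much in saying that no estimate will ever be reported. That is right: what is missing is a named summary and interval for the main analysis. Also, a fixed signed-rank test with a Hodges-Lehmann interval would remove the data-driven choice just as well. That is true too. The mean is preferred because it matches the planned sample-size inputs. A crossover model with a period term could estimate the same quantity.

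A reader might also infer that the rule inflates false positives. With 85% of patients about 3.5 points worse and 15% 20 points better (mean change zero), the rule with a signed-rank test rejects in about 26% of trials at n=25 and 46% at n=50. But the pseudo-median there is about −2.1 points, so the rank test is detecting a real shift in a different quantity. Nothing in the documents suggests that the dressing worsens leakage in most patients. The example shows that the target moves. It does not show a general type I error problem.

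**Conclusion.** The concern holds, as a prespecification gap. Section 13.1 lets observed normality choose the primary test, and no other section fixes a test, a summary measure or an interval. In the assumed 20%/80% mixture the cost is roughly 10 percentage points of power with a signed-rank alternative. It is far larger if the rank-sum test is applied literally: about 28%, against 61–64% (n=25) and 94% (n=50) for a fixed t-test. These figures rest on an assumed distribution, an assumed Shapiro-Wilk check and, for the rank-sum case, an assumed baseline SD. With near-normal differences and a signed-rank test the cost is negligible.

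A reader might infer that the main phase is already underpowered. The documents do not support that: no main-phase N, alpha or power exists yet, and the sample-size modification could still name a matching test. The supported statement is that N and analysis may not match unless the analysis is fixed first.

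**What to change.** Replace the sentence in 13.1 with one primary analysis: the mean within-patient difference in percent leakage (Tegaderm minus no alteration), with a two-sided 95% confidence interval and the paired t-based p-value, used whatever the distribution looks like. Name a paired signed-rank test with the Hodges-Lehmann estimate and interval, or a permutation test, as a sensitivity analysis, and remove the rank-sum test. Use a single prespecified method for each secondary outcome too, including the beard-length comparison. Base the main-phase sample-size modification on the primary analysis. For orientation, the 95% interval half-width is about 0.41 SD at n=25 and 0.28 SD at n=50.

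The cost is wording only, and the modification that the plan already requires for the sample size can carry it. The downside is some loss of power if the differences prove symmetric and heavy-tailed; the rank-based sensitivity analysis would show that case.

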### 3. Study Design

- 3.1. Our study design is a randomized prospective crossover trial in adult patients (>18 years), with circumferential perioral facial hair longer than 5 mm who will undergo elective non-cardiac surgery in the main adult operating rooms of the University of New Mexico Hospital.
- 3.2. Allocation concealment: Providers and subjects will be blinded to which method they will start with (control versus intervention) via envelope method prior to induction of general anesthesia.
- 3.3. Subjects who are consented to participate in the study will have facial hair measured as a continuous variable length (mm).
- 3.4. Mask ventilation operators will be confined to anesthesiology residents, anesthesiologist assistants (AA), and AA students all of whom are familiar with bag mask ventilation. Mask ventilation will occur using a two-handed Thenar-Eminence (TE) grip without the addition of an oropharyngeal airway. All operators will be instructed on how to perform this technique prior to patient enrollment. We will use Pressure Control ventilation mode on Anesthesia Ventilator machine (Dräger Perseus A500) set at 10 breaths per minute, I:E time of 1:2 and peak inspiratory pressure of 20 cm H2O, all of which are routine in our practice and within typical ranges at the national level. These are specified only in order to reduce practice variation not related to the intervention itself. An external pneumotachograph device and sensors (Phillips Respironics NM3™ respiratory profile monitor; Respironics CAPNOSTAT® Mainstream CO2 sensor) will be used to measure ventilation parameters ( Vtins; mL, VtExp; mL, PPins; cm H2O, Res; cm H2O/L/sec) with collected data electronically saved to a dedicated flash drive associated with the pneumotachograph .

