## Tegaderm™ Placement for Bag Mask Ventilation in the Bearded Patient

blockade to completion of one minute of mask ventilation with and without Tegaderm™ use. Patients will act as their own controls. Anesthesia induction and apnea will be defined as no voluntary respiratory effort and the absence of the eyelid reflex. Complete Neuromuscular blockade will be defined as Train of Four Ratio of **0/4** with neuromuscular monitoring at the *Corrugator Supercilii* muscle.

Once subjects are apneic and induced, **3** mask ventilation breaths will be administered in order to ‘acclimate’ the user to the mask and insure a proper thenar-eminence (TE) grip is being used. The randomized crossover trial will be started once complete neuromuscular blockade is verified. Every consecutive trial will alternate between starting with Tegaderm™ use and no alteration with patients acting as their own controls. Both no alteration and Tegaderm™ portion of exam will use the Resironics NM3™ (Resironics Deutschland, Herrsching, Germany) and CAPNOSTAT® 5 (Phillips Healthcare corporation, Eindhoven, The Netherlands) sensors to measure primary outcomes: Inspired tidal volumes (  $V_{t_{ins}}$ ; ml ), expired Tidal Volumes of End Tidal CO2 (  $V_{t_{Exp}}$ ; ml ) which will be used to determine predefined adequate BMV (Inspired Tidal Volume- Expired Tidal Volume difference of <15% defined as adequate) and secondary outcomes: within-patient differences between Tegaderm™ and no-alteration conditions for peak inspiratory pressures (  $PP_{ins}$ ; cm H2O ) and airway resistance (  $Res$ ; cm H2O/l/sec ) for 60 seconds, and facial hair grouping comparisons. The anesthesia machine will be set to deliver standardized pressure-controlled ventilation using common parameters: peak inspiratory pressure of 20 cm H2O, 10 breaths per minute, and an inspiratory-expiratory ratio of 1:2. These values are within common ranges used in standard practice, but may be modified during surgery as determined to be clinically appropriate by the attending anesthesiologist. General anesthesia will be maintained with sevoflurane 4-6% with 100% O2 at a rate of 6 liters per minute. Once data is gathered for the first part of the trial (no alteration or Tegaderm™), we will change our technique and collect data for second 60 seconds component of the trial in similar fashion to initial data collection.

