12.2.2. Study information

- 12.2.2.1. Level of the provider
- 12.2.2.2. Paralytic
- 12.2.2.3. Beard length (perioral)
- 12.2.2.4. Randomization result
- 12.2.2.5. Respiratory parameters

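### Secondary outcome 3 asks how far leakage change depends on beard length in mm, but the only planned analysis compares undefined beard groups

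*Combined protocol and SAP*

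**What the plan says.** - **Question asked.** Section 7.1 lists as secondary outcome 3: "Extent to which mask leakage change with Tegaderm™ depends on beard length". The same section defines leakage on a continuous scale, as the "difference between average inspired and expired tidal volumes, as a percentage of inspired volume".
- **Measurement.** Section 3.3 will have "facial hair measured as a continuous variable length (mm"). The data list in 12.2.2 holds one beard item, "Beard length (perioral"), and no category.
- **Analysis.** Section 13.1 says "Beard condition groups will be compared on the primary outcome", "with ANOVA or Kruskal-Wallis test, also depending on distribution normality". Section 12.1 has the matching phrase "facial hair grouping comparisons".
- **What is absent.** No section gives the number of groups, the cut-points or a rule for forming them. The only length threshold is the 5 mm eligibility limit in 4.2; every patient exceeds it, so it cannot separate groups. No regression or correlation on length is planned. The paired test in 13.1 addresses the overall within-patient difference, not its dependence on length.
- **The 15% remark.** The sentence in 13.1 also carries a parenthesis that calls a leakage difference above 15% significant. Section 12.1 uses 15% for something else, adequate ventilation: "Expired Tidal Volume difference of <15% defined as adequate".

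**The concern.** The outcome asks for the extent of a dependence, and the planned tests do not estimate one. ANOVA and Kruskal-Wallis treat short, medium and long beards as unordered labels. They can show that groups differ, but they give no change in leak per unit of length. Group means do describe the relation, but only as finely as the cut-points allow, and those are left open, so two analysts could follow 13.1 and report different results.

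At stake is the power and usefulness of one secondary result. If the relation is close to linear, grouping discards information that the trial already collects.

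**Working it through.** **Inputs.** The plan states no sample size, alpha, power or effect size for this outcome, so there is no figure of its own to reproduce. From the documents: 25 patients in the external pilot (5.2) and an initial authorization for up to 50 (5.3). The main-phase size is not set and no section pools the two phases, so 25 and 50 are reference points, not analysis sizes. Assumed: two-sided 0.05, correlation ρ between length and leakage change of 0.3, 0.4 or 0.5, and three equal groups.

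**Tests compared.** With r the sample correlation and k the number of groups:
- Slope: F = r²(n−2)/(1−r²), on 1 and n−2 degrees of freedom.
- Groups: F = [SS between/(k−1)] / [SS within/(n−k)], on k−1 and n−k degrees of freedom.

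**Step 1: linear relation, normally distributed length** (20,000 simulated trials per row).

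| n | ρ | Slope, power % | 3-group ANOVA, power % | Points lost |
|---|---|---|---|---|
| 25 | 0.3 | 31.2 | 18.5 | 12.7 |
| 25 | 0.4 | 52.4 | 32.0 | 20.4 |
| 25 | 0.5 | 74.7 | 49.5 | 25.2 |
| 50 | 0.3 | 57.2 | 36.5 | 20.7 |
| 50 | 0.4 | 84.2 | 62.7 | 21.5 |
| 50 | 0.5 | 96.7 | 85.7 | 11.0 |

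The loss is therefore about 11 to 25 points. Repeat runs agreed to about one point.

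Closed-form check for the slope: power ≈ Φ(atanh(ρ)·√(n−3) − 1.96). At n=50 and ρ=0.4 this is Φ(0.4236 × 6.856 − 1.96) = Φ(0.944) = 82.8%, close to the simulated 84%.

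The number of groups matters little: two groups give 63% and four give 60% at n=50, ρ=0.4. Kruskal-Wallis on three groups is 2 to 5 points below ANOVA.

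**Step 2: other shapes** (n=50; right-skewed lognormal length, log-SD 1; correlation 0.4 between the true shape and the change). Power in %:

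| True relation | Slope, log mm | Slope, mm | 3 groups |
|---|---|---|---|
| Linear in log mm | 83 | 68 | 63 |
| Linear in mm | 56 | 69 | 34 |
| Step at the median | 64 | 40 | 57 |
| Step at the 67th percentile | 61 | 53 | 64 |
| Rising in log mm to the median, then flat | 69 | 27 | 55 |

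Regression wins on either scale when the relation is linear in mm or log mm. For the steps and the plateau, the slope in mm falls below three groups. The slope in log mm stays ahead except for the step at the 67th percentile, which is itself a tertile cut-point. For a U-shape in log length, the log slope has 12% and three groups 20%; a squared term finds it in 74% on the log scale but in only 19% in mm.

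**Step 3: error rate with no relation.** Three groups formed from the sample quantiles of length, without reference to leakage, reject in 4.8 to 5.2% of trials.

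**The case against.** The case for leaving the plan alone has four parts.

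1. **A group comparison assumes no shape.** Step 2 shows that it can beat a straight line for steps and plateaus. This stands, and it rules out any claim that regression is better for every monotone relation.
2. **The illustrated sizes are not analysis sizes, and the correlations are assumed.** This stands too. The loss could be smaller in a larger main phase.
3. **Regression with a squared term and a Spearman correlation has its own freedom.** With no relation, at least one of the three is significant in 11 to 12% of simulated trials. This stands, and the remedy must say which result decides.
4. **It is one secondary outcome with no power or alpha assigned.** True. That sets the priority, but it does not make the test fit the question.

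Two stronger readings are tempting, and the documents support neither.

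- **A reader might infer that undefined groups inflate the false-positive rate.** Picking the best of two, three or four groups after seeing leakage would raise it to about 11%, but no section plans that. Groups formed from length alone hold 5%.
- **A reader might infer that leakage change will be cut at 15% into a yes/no outcome, with further loss of power.** The same sentence in 13.1 chooses between ANOVA and Kruskal-Wallis by normality, which presupposes an outcome that is not binary. The parenthesis is unclear and worth a clarifying sentence, but it is not evidence of dichotomisation.

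**Conclusion.** The concern holds as a mismatch between the question and the method. Secondary outcome 3 asks for a dependence on a continuous measurement, and the plan offers only an unordered comparison of groups that it never defines. The size, 11 to 25 points of power, is illustrative and rests on every assumption in Step 1, above all linearity and normally distributed length. It does not carry over to all shapes. The missing slope and interval do not depend on those assumptions: neither planned test provides them. The issue is power and a usable estimate, not type I error. It is worth correcting because the data are already being collected. It does not bear on the trial's main conclusion.

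**What to change.** In 13.1, with a matching phrase in 12.1:

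1. Make the single main analysis of secondary outcome 3 a linear regression of the within-patient change in percentage leak on continuous beard length, reporting the slope with its 95% CI. Name the percentage definition in 7.1 explicitly, because 1.1 expresses leak in mL.
2. Fix the scale (mm or log mm) from the distribution of length alone, before leakage is examined.
3. State that a squared term and a Spearman correlation are supportive only and do not change the conclusion drawn from the slope test.
4. Make any length groups descriptive, with cut-points set without reference to leakage.
5. State in one sentence that the 15% remark is not a test criterion for this analysis.

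**Cost.** A few sentences, which can go into the modification that 5.2 already requires for the main phase. No new data are needed. The downside is some loss of power if the true relation is a step at a cut-point, a plateau or a U-shape, or if the chosen scale is wrong. For the two linear shapes in Step 2 the wrong scale costs 83 − 68 = 15 points or 69 − 56 = 13 points, and for the plateau 69 − 27 = 42 points. The choice of scale therefore deserves care.

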## 2. Background

- 2.1. Bag mask ventilation (BMV) is an essential skill for health care professionals involved in airway management. This ubiquitously needed skill can be lifesaving in emergent situations but is frequently impeded by various patient characteristics. If incorrectly approached and applied, BMV may be ineffective and lead to hypoxia, hypercarbia  or pulmonary aspiration . Difficult mask ventilation (DMV) pathophysiology is well described by El-Orbany et al as having two broad components: 1) operator or technique related and 2) airway related factors. Independent risk factors for DMV include the presence of a beard, increased BMI (> 26 kg/m^2), edentulism, age >55 years, history of snoring, Mallampati III or IV, male gender, limited mandibular protrusion, and airway masses . In recent years, there has been a joint effort amongst emergency physicians, anesthesiologists, and pre-hospital clinicians to improve our understanding of BMV, standardize our approach and teach optimization with a surplus of corrective measures when faced with difficult BMV . The most basic optimizing maneuvers such as switching from a single hand to two-handed thenar-eminence grip has shown promising objective results . More novel approaches to improve facemask seal have been suggested such as keeping dentures in mouth or packing the mouth with gauze during induction of general anesthesia of the edentulous patient , and employing ergonomically designed facemasks , accessories , and intraoral masks  to reduce operator error and grip fatigue.

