12.2.1. Patient background information

- 12.2.1.1. Past medical history
- 12.2.1.2. Surgery Type
- 12.2.1.3. Race
- 12.2.1.4. Obstructive Sleep Apnea History
- 12.2.1.5. Mallampati score
- 12.2.1.6. Age
- 12.2.1.7. Weight
- 12.2.1.8. Height
- 12.2.1.9. Body Mass Index

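### The beard-length question compares different, unrandomised patients, but 13.1 plans no adjustment, so BMI, age or Mallampati class could pass for a beard-length effect if they also alter the dressing's benefit

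*Combined protocol and SAP*

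**What the plan says.** Section 7.1 lists as its third secondary outcome the "Extent to which mask leakage change with Tegaderm™ depends on beard length". The same section says of the primary outcome that "Patients will serve as their own controls".

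Section 13.1 answers the beard-length question in one sentence: "Beard condition groups will be compared on the primary outcome", and this is to be done "with ANOVA or Kruskal-Wallis test, also depending on distribution normality". Section 12.1 adds only "facial hair grouping comparisons". Neither place defines the groups or gives cut points, although section 3.3 records beard length as a continuous measurement in mm. No section plans a regression, ANCOVA, stratification or matching for this outcome.

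Section 2.1 opens its list of risk factors with "Independent risk factors for DMV include the presence of a beard, increased BMI" and goes on to edentulism, age above 55, snoring and Mallampati class III or IV. Section 12.2.1 collects Mallampati score, age, sleep apnoea history and, as its last item, "12.2.1.9. Body Mass Index". Section 13 does not mention any of them.

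**The concern.** The crossover gives a clean comparison of Tegaderm with no alteration, because both conditions are observed in the same patient. It gives no such protection to the question of whether the change in leakage varies with beard length. That question sets one group of patients against another, and patients with long beards may differ from those with short beards in build, age or airway class. One-way ANOVA and Kruskal-Wallis, as planned, cannot separate these influences.

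At stake is the statement about which patients the dressing helps most. The background (2.3) hopes the study will inform guidelines, and a gradient by beard length would be read in that light. Confounding could create a gradient that is not there or hide one that is.

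**Working it through.** The plan states no figure for this comparison, so there is nothing to reproduce. Sections 5.2 and 13.2 say the data for a sample-size calculation are not available.

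**Inputs from the documents.** Pilot size 25 (5.2, 13.2); initial authorisation up to 50 (5.3); 60 as a recruitment remark in 9.3. The main-phase size is undecided. Test: ANOVA or Kruskal-Wallis on groups (13.1).

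**Assumptions, not in the documents.** Three equal-sized beard-length groups; two-sided 5% level; one factor such as BMI; correlation *a* of the factor with beard length, 0 to 0.4; correlation *b* of the factor with the within-patient leakage change, 0.3 to 0.5; no true effect of beard length; normal variables.

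**Step 1: when can a factor confound?** Write leakage in patient *i* as L0 without the dressing and L1 with it. The outcome is D = L0 − L1.
- If a factor C adds the same amount γC to both, then D = (L0 + γC) − (L1 + γC) = L0 − L1. It cancels. In simulation the ANOVA rate stays at about 5% at all three sample sizes, even with *a* = 0.5.
- If the dressing removes a proportion p of baseline leakage, then D = p(L0 + γC), and C remains in the outcome. For illustration, take p = 50%, *a* = 0.5 and baseline leakage 30 + 10C plus noise of SD 8, with noise of SD 6 on the change. The ANOVA rate is then 18%, 34% and 41% at n = 25, 50 and 60. This implies *b* = 5/√(25 + 16 + 36) = 0.57, so it lies beyond the main range below and serves only to show the mechanism.

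**Step 2: size of the spurious association.** With no true beard effect, beard length and leakage change still correlate at *a* × *b*: 0.2 × 0.3 = 0.06; 0.3 × 0.5 = 0.15; 0.4 × 0.5 = 0.20. The association does not shrink with sample size, so the false-positive rate rises as enrolment grows.

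**Step 3: false-positive rate of the planned ANOVA** (simulation, 20,000 runs per setting):

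| *a* / *b* | n = 25 | n = 50 | n = 60 |
|---|---|---|---|
| 0 / 0.3-0.5 | 5% | 5% | 5% |
| 0.2 / 0.3 | 6% | 6% | 6% |
| 0.3 / 0.5 | 8% | 12% | 13% |
| 0.4 / 0.5 | 10% | 18% | 21% |

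Kruskal-Wallis runs slightly lower. Adjusting for the factor returns the rate to about 5% in every setting.

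**Step 4: cost of adjusting.**
- Lost degrees of freedom: the ratio of 97.5% t-quantiles with three more terms is 1.008 at n = 25 (20 versus 23 df) and 1.001 at n = 60.
- Collinearity, in the least favourable corner (*a* = 0.4, *b* = 0.3, one factor): the standard error of the adjusted slope relative to the unadjusted one is √[(1 − 0.09) / ((1 − 0.16)(1 − 0.0144))] = √(0.91/0.828) = 1.05, so about 5% wider. By simulation it is nearer 8% at n = 25. At most other settings the adjusted interval is narrower, because the factor explains part of the outcome.

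**The case against.** The strongest objection is that the outcome is already a within-patient change. Section 2.1 lists risk factors for difficult mask ventilation, which concerns the level of difficulty; nothing there says that they alter what the dressing achieves, and the documents do not show that any of them goes with beard length. A reader might infer that being a listed risk factor is enough to confound. It is not: both links are needed, and with either one absent the planned test holds its 5%. This stands, and it is why the point is conditional.

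A reader might also infer a false-positive rate of up to about a third. A simple slope test on continuous beard length does reach 34% at n = 60 in the most adverse corner, but the plan contains no such test. Three-group ANOVA reaches 21% there, and four groups about 19%.

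The question can also be read as descriptive. A clinician sees the beard, so the unadjusted association is a legitimate answer to how the change varies with beard length. That stands, and the unadjusted result should be kept beside the adjusted one.

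Design features narrow the scope. Section 4.3 excludes BMI of 50 or more, previously documented difficult mask ventilation and airway obstruction; grip and ventilator settings are standardised. These reduce variation in the named factors but do not remove it.

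Finally, a reader might infer that edentulism goes unrecorded. It is not itemised in 12.2.1, but it could appear under past medical history, so the documents do not settle this.

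**Conclusion.** The point holds in conditional form and is minor. The beard-length comparison is between patients and unrandomised, and the planned tests adjust for nothing, although three factors the protocol itself names as relevant are collected. Whether this biases the result depends on two links the documents do not address: the factor's relation to beard length and its relation to the size of the Tegaderm effect. Over the assumed ranges the false-positive rate runs from about 5% (no confounding) to 10%, 18% and 21% at 25, 50 and 60 patients. These figures illustrate one factor and three groups; they do not predict this trial's result.

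A reader might extend the point to the trial's main conclusion. The documents do not support that: the primary comparison is within patients, and differences in patient characteristics do not undermine it in this way.

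**What to change.** In 13.1, replace the group comparison for the third secondary outcome with a linear regression of the within-patient leakage change on beard length in mm. Report two slopes, each with a 95% CI: one unadjusted, and one adjusted for BMI, age and Mallampati class as a single term (I-II versus III-IV). Label both observational and exploratory. Keep a rank-based check if residuals are clearly non-normal. The two slopes should be read together, because the unadjusted slope on its own is more exposed to confounding than the planned ANOVA.

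The cost is one model statement and three degrees of freedom, with possible widening of about 5% from collinearity (a little more in small samples). On the 25 pilot patients alone the adjusted slope would be imprecise; four slopes and an intercept leave 20 residual degrees of freedom. Adjustment deals only with measured factors. Section 13 could be revised in the modification already due for the main-phase sample size. Itemising edentulism in 12.2.1 is optional and costs one form field.
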